9. STUDY EVALUATIONS

9.1. Study Procedures

9.1.1. Overview

Evaluation of the safety/tolerability of the vaccine regimen will include vital signs, physical assessment by study-site personnel, ECGs, clinical laboratory test data and subject reports on signs and symptoms following vaccinations. Additional visits may be required if, in the investigator's opinion, further clinical or laboratory evaluation is needed.

Each subject will be provided with a thermometer, ruler and subject diary to measure and record body temperature (tympanic or oral) and solicited local (at injection site) and systemic events. The diary includes instructions on how to capture the data and grading scales to assess severity of the symptoms. Study staff are responsible for providing appropriate training for diary completion to avoid missing or incorrect data. The subject diary will be reviewed by the study personnel at visits indicated in the [Time and Events Schedule](#).

The [Time and Events Schedule](#) summarizes the frequency and timing of safety and immunogenicity measurements applicable to this study.

The total blood volume to be collected from each subject over the entire study will not exceed 470 mL unless additional blood samples are required for safety reasons. The maximum volume of blood to be drawn at any given visit will be 70 mL.

9.1.2. Visit Windows

For the following visits, windows will be allowed as indicated:

Visit Day	Window	Primary Purpose
Day -25	± 1 day	3-day post-vaccination, telephone call for safety
Day -21	± 2 days	7-day post-vaccination safety only visit
Challenge	24-90 days	Time between vaccination and viral challenge
28 days post-challenge	± 4 days	Safety and immunogenicity
6 months post-vaccination	± 14 days	Final visit (SAE follow-up)

9.1.3. Screening Phase

Screening for eligible subjects will be performed between 56 days to 3 days prior to vaccination. Historical pre-screening data from hVIVO's ethics committee-approved screening protocol can be used to confirm eligibility if performed within this time frame.

Only healthy subjects without acute illness or fever and complying with the inclusion and exclusion criteria specified in Section 4 will be included in the study. The investigator will provide detailed information on the study to the subjects and will obtain written informed consent prior to each subject's participation in the study.

The following evaluations will be performed to determine eligibility requirements as specified in the inclusion and exclusion criteria:

- Physical examination including vital signs measurement (respiratory rate, heart rate, supine systolic and diastolic blood pressure and body temperature) and height and weight
- Demographic information
- Medical history, including smoking habits
- Review of pre-study medications
- Review of inclusion/exclusion criteria
- 12-lead ECG
- Sero-susceptibility for RSV (neutralization assay)
- Serology testing (HIV type 1 or type 2, hepatitis B, hepatitis C)
- Blood sampling for hematology and biochemistry laboratory testing (laboratory tests at screening are to be done within 56 days of randomization)
- Urine sample for urinalysis
- Nasopharyngeal swab tolerability testing
- Nasal wash tolerability testing
- Spirometry
- All female subjects: serum β -hCG pregnancy testing
- A urine screen for drugs of abuse and an alcohol breath test
- Overall eligibility

Historical pre-screening data collected through the ethics committee-approved hVIVO screening protocol within 56 days (90 days for viral serology) to 3 days prior to vaccination may be used for screening procedures. Historical pre-screening data obtained prior to this window can be re-assessed any time from 40 days to 3 days prior to vaccination.

General eligibility for this clinical study will be dependent on results of laboratory tests and the medical assessment. Study subjects who qualify for inclusion based on the medical history, physical examination, and laboratory results will be contacted and scheduled for enrollment and vaccination. If necessary, the screening visit may be split into several visits. Screening should occur between 56 days to 3 days before vaccination.

Subjects with laboratory values not meeting eligibility criteria at the screening visit may have one repeat testing at the discretion of the investigator if the abnormality is not clinically significant and may be a testing aberrancy. Enrollment of a subject with laboratory values representing toxicity Grade 1 is allowed if the investigator considers the values not to be clinically significant and reasonable for the population under study. Details on toxicity grade assessment are provided in Section 12.1.3.

After laboratory data, medical history, physical examination, ECG and nasopharyngeal swab/nasal wash tolerance data have been reviewed for completeness and adherence to inclusion and exclusion criteria, the subject can be deemed eligible for the study.

Unsolicited AEs will be recorded on the AE page of the eCRF from ICF signature until 28 days after vaccination, and from the entry into the Unit until 28 days after challenge. SAEs will be collected from ICF signature until 6 months after vaccination (ie, the end of the study).

9.1.4. Vaccination Phase

9.1.4.1. Vaccination

Randomization/Vaccination

After re-check of inclusion and exclusion criteria^a, a urine screen for drugs of abuse, an alcohol breath test, abbreviated physical examination (at the discretion of the investigator) and measurement of vital signs, eligible subjects will be randomized as described in Section 5. If medical status and/or physical examination suggest significant changes have occurred since screening, the laboratory tests will be repeated and the vaccination visit rescheduled, or the subject excluded from the study if he/she fails to meet the inclusion and exclusion criteria. Pre-dose samples for baseline immunogenicity assessments and for clinical laboratory testing will be collected. All women must have a negative urine pregnancy test pre-dose. Before vaccination, the investigator must check for any symptoms of an acute illness or body temperature ≥ 37.8 °C. In such a situation, the subject may be re-screened (if vaccination number not assigned), or withdrawn at the discretion of the investigator. *Note*: the minimum time between vaccination and challenge is 24 days.

Administration of study vaccine. Vaccination will occur 28 days before challenge (window is not less than 24 or more than 90 days).

^a To include exclusion criteria 1, 7, 8, 9, 10, 14 and 16.

Subjects will be closely observed for a minimum of 30 minutes post-vaccination to monitor for the development of any acute reactions, or longer if deemed necessary by the investigator. Any unsolicited, solicited local or systemic AEs and vital signs will be documented in the eCRF by study-site personnel following this observation period.

Subjects will be provided with a subject diary, thermometer, and ruler to measure and record body temperature, solicited local and systemic AEs for 7 days post-vaccination.

9.1.4.2. Post-vaccination Follow-Up

Sentinel Subjects: 48 Hours Post-first Vaccination

At 48 hours after the first vaccination, a telephone call will be made to the two sentinel subjects only to collect safety information (solicited and unsolicited AEs, SAEs and concomitant medications).

3 and 7 days post-vaccination

The visit at 3 days post-vaccination will be a telephone call to check subject diaries and to collect safety information (solicited and unsolicited AEs, SAEs and concomitant medications).

The visit at 7 days post-vaccination will include an abbreviated physical examination (at the discretion of the investigator), vital signs measurement, and recording of any AEs/SAEs and concomitant medications. Samples for clinical laboratory testing will be collected. Subject diaries will be reviewed and collected. If this visit occurs before the end of the post-vaccination diary period, review of the diaries will still take place, but diaries will be returned by subjects at the next visit (ie, on admission to the Unit for the challenge phase).

9.1.5. Viral Challenge Phase

9.1.5.1. Entry to the Quarantine Unit

Subjects will enter the quarantine Unit either one or two days before the viral challenge, to acclimatize and perform entry assessments. The following assessments can take place on either day: complete physical examination, including body weight, relevant medical information since vaccination, vital signs and spirometry, samples for clinical laboratory tests (including cardiac enzymes), ECG, blood samples for immunogenicity assessments, spirometry, and recording of any unsolicited AEs/SAEs and concomitant medications. Nasopharyngeal swabs and nasal wash samples will be collected to screen for respiratory virus and for RSV pre-F antibody assessment, respectively, and blood samples will be taken to determine sero-susceptibility for RSV for post-hoc reconfirmation (neutralization assay).

The SSC will be filled out by the subject and reviewed by the attending physician. Tissues for tissue counts and mucus weight will be distributed on Day -1. The first 24-hour collection will start on Day -1; tissue counts and mucus weights will be determined on Day 0.

A serum pregnancy test (β -hCG) will be performed for all female subjects. A urine drug screen, a urine cotinine test, and an alcohol breath test will be performed.

Throughout the challenge phase of the study from entry to the Unit until discharge, subjects will stay in individual isolation rooms to minimize cross-contamination between subjects.

Before challenge inoculation on Day 0, the subject's clinical status will be checked, including any available laboratory results or receipt of additional medical records.

9.1.5.2. Challenge

On Day 0, intranasal challenge with RSV-A Memphis 37b virus will occur for all subjects. The site physician, or inoculation-trained member of the site medical team, will inoculate each subject intranasally with 0.8 mL of virus, delivered by pipetting 2x200 μ L of virus per nostril. The target day for challenge is 28 days after vaccination (window is not less than 24 or more than 90 days). The longer window will be for the few overflow subjects that are available for challenge in a subsequent cohort.

Additionally, all post-challenge procedures per Section 9.1.5.3 will be carried out apart from collection of a nasal wash sample and ECG.

The inoculum virus titer is determined in an infectivity (plaque) assay, the titer is reported in plaque forming units per mL (PFU/mL). The challenge dose is approximately $4\log_{10}$ PFU. One vial of challenge virus will be provided for each subject. Full details of inoculation procedures will be provided in the Analytical Plan.

9.1.5.3. Post-challenge

On each of the 11 days after the challenge, procedures will include a directed physical examination, spirometry and monitoring of vital signs. Nasal wash samples will be taken every 12 (\pm 1) hours from the second day after challenge until discharge. The SSC will be filled out three times a day by the subject and reviewed by the attending physician. Tissue counts and mucus weight will be determined for each 24-hour interval. ECGs will be carried out, and blood samples collected for clinical laboratory tests (cardiac enzymes only) on Days 3, 7 and 11. Any unsolicited AEs/SAEs and concomitant medications will be recorded.

9.1.5.4. Discharge from the Unit

On Day 12, subjects will only be discharged when no detectable virus is present (negative RVAT). If symptoms are present, but no virus is detected (negative RVAT), discharge will be at the investigator's discretion. If appropriate, subjects may reside in quarantine for an additional night or longer before discharge.

Procedures will include a complete physical examination including body weight, vital signs and spirometry, collection of nasopharyngeal swabs, and completion of the SSC by the subject and review by the attending physician. Tissue counts and mucus weight will be determined for the final 24-hour interval, and nasal wash samples will be collected for RSV pre-F antibody

assessment. A urine pregnancy test will be performed for all female subjects. Any unsolicited AEs/SAEs and concomitant medications will be recorded, and blood samples collected for clinical laboratory tests (hematology and biochemistry only).

9.1.6. Day 28 Post-challenge

The visit at 28 days post-challenge will include an abbreviated physical examination (at the discretion of the investigator), and vital signs measurement. Blood samples for immunogenicity assessments will be collected. Any unsolicited AEs/SAEs and concomitant medications will be recorded, and blood samples collected for clinical laboratory tests (hematology and biochemistry only). A urine pregnancy test will be performed for all female subjects.

9.1.7. Final Visit

The final visit at 6 months post-challenge will be a telephone call to record SAEs and concomitant medications associated with any SAE.

9.1.8. Early Withdrawal – Early Exit Visit

For those subjects who are unable to continue participation in the study, but who do not withdraw consent, an early exit visit will be conducted as soon as possible. In the event of early withdrawal from the study, all procedures required at the Day 28 visit (Section 9.1.6) will be performed. Samples for immunogenicity assessments will only be collected if the early exit is at least 14 days after the previous blood draw for immunogenicity. Samples for safety laboratory testing will only be collected if the early exit is within 7 days of the vaccination. Solicited AEs will be recorded if the early exit visit occurs within 7 days of vaccination. Any unsolicited AEs/SAEs and concomitant medications will be recorded. At the early exit visit, a serum pregnancy test (β -hCG), not a urine test, will be performed for all female subjects.

Precautions for any subject leaving the challenge Unit are listed in Section 4.4.

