Risks Associated with the Human Challenge Model

Healthy adult subjects will be recruited as they are best suited to tolerate inoculation of the virus.

Severe complications tend to occur almost exclusively in infants, the elderly, and persons of any age with chronic co-morbidities or who are significantly immune-compromised. Qualified doctors and nurses in the quarantine Unit will manage any symptoms.

As a consequence of the RSV-A Memphis 37b inoculation, AEs (serious or non-serious) related to RSV infection commonly occur. These anticipated AEs are related to, but not limited to, rhinitis, rhinorrhea, nasal congestion, sneezing, nasopharyngitis, ear ache, malaise (tiredness), cough, shortness of breath, muscle and/or joint pain, headache, fever, nasal blood spotting, and

upper respiratory tract infection. In addition, laboratory abnormalities related to RSV viral infection may occur such as, but not limited to, hematologic changes (increases in white blood cell [WBC] count and changes in differential values) and increased levels of inflammatory markers (eg. C-reactive protein).

The study virus, like many viruses, can cause more substantial health issues such as myocarditis. However, the chance of this resulting in permanent changes is rare as most cases are minor and resolve without sequelae. In over 500 subjects inoculated with the study virus by hVIVO, clinical laboratory tests in 2 subjects have shown changes suggestive of myocardial inflammation: both cases returned to normal without treatment and were not associated with specific symptoms or ECG changes.

It is unlikely that subjects will transmit RSV virus to their close contacts after they have been released from the quarantine Unit. After infection with RSV, infectious virus will be present in the subject's nose for several days, but it is not expected to be present in the subject's nose at the time of discharge from the Unit. This is because the usual duration of time that RSV remains infective in adults is several days shorter than the time they will spend in the Unit in isolation.⁹

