Blood will be collected for sero-susceptibility (neutralizing antibody to RSV-A Memphis 37b) within 90 days of vaccination and on entry to the Unit. Blood and urine will be collected for laboratory safety assessments within 56 days of vaccination, pre-vaccination, at 7 days post-vaccination and prior to challenge on Day -1 or Day -2. Blood will additionally be collected for biochemistry and hematology assessments at discharge from the quarantine Unit and at 28 days post-challenge. Blood for assessment of cardiac enzymes will also be collected on Days 3, 7, and 11.

Blood samples for humoral and cellular immunity will be collected pre-vaccination, 1-2 days prior to challenge, and at 28 days after challenge. *Note:* blood samples for immunogenicity

[figure not shown]
assessment will be collected from all subjects whether subjects are challenged or not (ie, including “overflow” subjects). Blood draws for overflow subjects who are not challenged will occur at 28 days post-vaccination and again 28 days later. Overflow subjects who are challenged in a later cohort will also have blood draws at the time of challenge and 28 days after challenge.

RSV pre-F antibody will be assessed on the day before challenge and at discharge from the Unit from nasal wash samples.

An internal data review committee (DRC) will be commissioned for this study, the members of which consist of a clinician with expertise in vaccines and infectious diseases, a medical safety officer and a statistician, none of whom will be part of the study team or involved in the conduct of the study. The DRC will meet if, in the judgment of the investigator and/or the sponsor’s SRP, a significant or unexpected safety event occurs.

The end of the study will be the last subject’s last visit by telephone at 6 months after vaccination.

A diagram of the study design is provided in [Figure 1](#).

Figure 1: Schematic Overview of the Study

* Historical pre-screening data collected through the ethics committee-approved hVIVO screening protocol within 56 days to 3 days prior to vaccination (90 days for viral serology) may be used for screening procedures. Historical pre-screening data obtained prior to this window can be re-assessed any time from 40 days to 3 days prior to vaccination.

RVAT = rapid virus antigen test

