9.2.6.2. Clinical Laboratory Tests

Blood and urine samples for laboratory safety assessments will be collected for screening up to 56 days prior to vaccination, pre-vaccination, 7 days post-vaccination, and prior to challenge on Day -1 or Day -2. Blood samples will additionally be collected at discharge from the quarantine Unit and at 28 days post-challenge. The following tests will be performed by a local laboratory (*parameters only measured at screening):

- **Hematology Panel**

- platelet count.
- white blood cell (WBC) count (absolute)
- WBC differential
 - neutrophils
 - lymphocyte
 - monocytes
 - eosinophils
 - basophils
- red blood cell (RBC) count
- reticulocyte count (% and absolute)
- hemoglobin
- hematocrit
- mean corpuscular volume (MCV)
- mean corpuscular hemoglobin (MCH)
- MCH concentration (MCHC)

- **Biochemistry Panel**

- sodium
- potassium
- glucose (random)
- albumin

chloride
bicarbonate
calcium
uric acid
total protein
creatinine
total, direct, and indirect bilirubin
inorganic phosphate
blood urea nitrogen
C-reactive protein
gamma glutamyl transferase
alkaline phosphatase
alanine transaminase
lactate dehydrogenase
aspartate transaminase
urea

- **Cardiac Enzymes** (done together with ECGs on admission, and on Days 3, 7 and 11)

Troponin T
creatinine kinase

- **Urinalysis** – dipstick for:

specific gravity
pH
glucose
protein
blood
ketones
appearance
color
nitrite
urobilinogen
bilirubin
leucocytes

A repeat urinalysis will be performed in the event of a positive dipstick test. Microscopic reflex testing will be carried out if the repeat urinalysis dipstick test is also positive.

Review and Grading of Laboratory Data

The investigator must review each laboratory result, document this review and assess systematically any clinical significance. The laboratory reports must be filed with the source documents.

Laboratory values will be initially evaluated by the investigator according to local laboratory criteria. Abnormal values outside the local laboratory range of normal will be graded according to the FDA Guidance document “Toxicity Grading Scale from Healthy Adult and Adolescent Volunteers Enrolled in Preventive Vaccine Clinical Trials” (see [Attachment 1](#)). Laboratory values within local laboratory normal limits will not be FDA graded and will be considered as normal.

Reporting Laboratory Abnormalities as AEs

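### Early-exit safety bloods are limited to 7 days after vaccination, so a challenged subject who leaves before the Day 28 visit with consent intact has no hematology or biochemistry scheduled at exit

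*Protocol*

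**What the plan says.** Protocol Section 9.1.8 covers subjects who cannot continue but "who do not withdraw consent, an early exit visit will be conducted as soon as possible". It first applies every procedure of the Day 28 visit to that exit visit, and Section 9.1.6 includes hematology and biochemistry among those procedures. It then narrows two of them. Immunogenicity blood is drawn only if at least 14 days have passed since the previous immunogenicity draw. For safety bloods the rule is: "Samples for safety laboratory testing will only be collected if the early exit is within 7 days of the vaccination".

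Section 9.1.5.2 fixes the interval from vaccination to challenge: "window is not less than 24 or more than 90 days".

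A challenged subject who completes the schedule has two post-challenge panels. Section 3.1 says: "Blood will additionally be collected for biochemistry and hematology assessments at discharge from the quarantine Unit and at 28 days post-challenge". Section 9.2.6.2 agrees: "Blood samples will additionally be collected at discharge from the quarantine Unit and at 28 days post-challenge". Cardiac enzymes alone are drawn on Days 3, 7 and 11 (Section 9.1.5.3).

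Subjects who withdraw consent come under Section 10.2 instead. They are offered one safety exit visit, for which no laboratory tests are listed.

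**The concern.** A seven-day limit suits the vaccination phase: it matches the post-vaccination laboratory visit and the diary period. Applied to the whole study, it removes safety bloods from every exit visit after challenge, which is when new laboratory changes are expected. Section 1.3.4 says that after inoculation "laboratory abnormalities related to RSV viral infection may occur such as, but not limited to, hematologic changes", and it also names raised inflammatory markers. Clinical laboratory results are part of the secondary safety endpoint (Section 2.1.2). SAP Section 7.2 takes the worst emerging grade over all measurements in a period, so a missing panel removes one chance to record an abnormality.

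Leaving with consent intact is foreseeable. Section 10.2 withdraws subjects for repeated non-compliance, and Section 5 withdraws a subject whose code is broken at the site. For such a subject the exit visit is the last planned contact at which a new laboratory abnormality could be found.

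**Working it through.** The plan gives no figure for this point. The check compares day windows, counts panels and adds blood volumes.

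**1. Can a challenged subject meet the seven-day condition?** Inputs: 7 days (Protocol 9.1.8); challenge 24 to 90 days after vaccination (9.1.5.2); Day 28 visit window ±4 days (9.1.2).

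- Earliest challenge: 24 − 7 = 17 days past the limit.
- Latest challenge: 90 − 7 = 83 days past the limit.
- Latest exit before the Day 28 window closes: 90 + 28 + 4 = 122 days after vaccination.

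Safety bloods are allowed on days 0–7 after vaccination. Exits of challenged subjects fall on days 24–122. The ranges do not overlap, so 0 panels are scheduled at exit for any challenged subject. The gap runs from Day 0 to Day 28 after challenge, or to Day 28 + 4 = Day 32 with the window.

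**2. Which sentence of 9.1.8 governs?** The opening sentence carries over all Day 28 procedures. The later one is specific to safety laboratory samples and uses the word only, so it governs. If a site followed the opening sentence instead, 9.1.8 would be giving two conflicting instructions. The Schedule's notes contain a seven-day condition too. In the extracted text its symbol also appears against the screening sample, where it makes no sense, so I do not rely on it.

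**3. Post-challenge panels obtained, out of 2**

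| Time of exit | As written | With the fix |
|---|---|---|
| Before Day 12, release treated as discharge | 1 | at least 1 |
| Before Day 12, release not treated as discharge | 0 | 1 |
| After discharge, before the Day 28 visit | 1 | 2 |
| After the Day 28 visit | 2 | 2 |

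The second row arises only because Sections 3.1 and 9.2.6.2 tie the first panel to discharge, while Section 9.1.5.4 describes discharge as a Day 12 procedure.

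**4. Is blood already drawn at the exit visit?** Every female subject has a serum pregnancy test there (9.1.8). The last immunogenicity draw before challenge is on Day −2 or −1, so the 14-day condition is met from −2 + 14 = Day 12 or −1 + 14 = Day 13. A subject leaving from then until Day 28 gives 10 + 50 = 60 mL for immunogenicity, but no 10 mL safety sample.

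**5. Does an added draw fit the volume limits?** The Schedule's cumulative row reproduces: 10 + 70 + 10 + 70 + 30 + 10 + 70 = 270 mL.

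- Exit visit: 10 safety + 10 humoral + 50 cellular = 70 mL. This is the figure in the Early Exit column and equals the per-visit maximum (9.1.1).
- Exit before Day 12: 190 (after the Day 3, 7 and 11 draws) + 10 = 200 mL.
- Exit between discharge and Day 28: 200 + 70 = 270 mL, the same as a completer.

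Both totals are below the 470 mL study limit. The budgeted 70 mL cannot arise under the present rules: safety blood needs an exit within 7 days of vaccination, and immunogenicity blood needs at least 14 days since a previous draw, the first of which is on the vaccination day. The most that can be drawn now is 60 mL.

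**The case against.** The strongest reply is that early leavers are not abandoned. Section 5 requires a subject withdrawn after site unblinding to be followed as appropriate. Section 10.2 asks for observations to be completed as fully as possible and for a final evaluation. Section 9.1.1 allows extra visits and exempts additional safety bloods from the volume limit. Clinically significant abnormalities are followed to resolution (9.2.6, 9.2.6.2). The exit visit still includes vital signs, adverse event recording and a pregnancy test. Myocarditis, the more serious risk named in Section 1.3.4, is watched by cardiac enzymes on admission and by enzymes with ECG on Days 3, 7 and 11 while the subject is in the Unit. All of this stands and limits the consequence, but none of it schedules a hematology or biochemistry panel, and an abnormality must be detected before it can be followed.

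The limit may also be intended. Seven days matches the last vaccine-safety laboratory visit and the solicited-event rule beside it in 9.1.8, and Section 9.2.6.2 ties laboratory adverse event capture to 28 days after vaccination. That is plausible, but no rationale is stated. Equally, a reader might infer an oversight because Amendment 1 added the discharge and Day 28 panels without listing 9.1.8 among the sections affected. The amendment log is context and does not prove an error.

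Finally, on the ordinary reading, anyone leaving the Unit is discharged and has the first panel. That stands, so the usual loss is one panel.

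**Conclusion.** The point holds as a minor safety-design gap. No challenged subject can have hematology or biochemistry scheduled at an early exit visit under 9.1.8 as written. The usual loss is one of two post-challenge panels. It rests on the specific sentence in 9.1.8 overriding the general one.

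Two stronger readings are not supported:

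- A reader might infer that an early leaver has no laboratory assessment after challenge. That needs the site to treat release from the Unit as something other than discharge, which the documents neither state nor rule out. Enzyme draws before the exit and unscheduled bloods also remain.
- A reader might infer that the reported safety percentages would be distorted. The documents give no number of leavers. It may be zero, so no such effect can be claimed.

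Safety is analyzed descriptively, and the efficacy analysis is unaffected.

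**What to change.** Replace the sentence in 9.1.8 with wording such as: *Safety laboratory samples are taken at early exit if the exit is within 7 days of vaccination, or after viral challenge and before the 28-day post-challenge visit (hematology and biochemistry; cardiac enzymes added if the exit is during quarantine).* Match this in the Early Exit column of the Schedule. The added window starts at challenge because a full panel is already drawn on admission to the Unit. The enzyme clause reflects the two subjects, among more than 500 inoculated, whose laboratory changes suggested myocardial inflammation without specific symptoms or ECG changes (1.3.4).

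Optionally, offer the same draw at the Section 10.2 safety exit visit, which the subject may refuse. If the present limit is intended, a one-line reason in 9.1.8 would be enough.

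The cost is one sentence, one Schedule note and, if the option is taken, one clause in 10.2, plus about 10 mL of blood from a few subjects at a visit already planned.
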